#### 18. EFFICACY

Specific efficacy variables for this study are listed in Section 22.2. The following describes the collection of some variables in detail.

# 18.1. Bleeding

The incidence of bleeding treated with FVIII replacement infusion(s) will be obtained from Subject Diaries and medical records. Where relevant, investigators (or designee) and monitors will ensure that there is consistency between the subject's medical record and/or Subject Diaries and the electronic case report forms (eCRFs). Such bleeding episodes will not be reported as AEs although the concomitant events associated with a bleed may be reported as an AE if appropriate (eg, a fracture). In the rare instance in which a bleeding episode also meets the criteria for a Serious Adverse Event, then the bleeding episode should be recorded as an AE. Only bleeding episodes that are considered serious and meet the SAE criteria should be listed on the AE case report form (CRF) page. If the bleeding episode qualifies as an SAE and is treated with study drug, then in addition to recording the bleed event on the AE eCRF, the bleed event should also be recorded on the Bleed log as there is information captured on the Bleed log that is not captured on the AE eCRF (eg, infusion information and response to study drug).

Both spontaneous bleeding episodes and traumatic bleeding episodes will be collected.

## 18.1.1. Types of Bleeding

For the purposes of this study, a bleed treated with study drug will be classified as either spontaneous or traumatic. The subject's diary or medical record will serve as the source document for bleeding episodes while on study. Investigators (or designee) and/or monitors will review the Subject Diary and medical records to assist in classification if necessary. The criteria for spontaneous and traumatic bleeds are described below.

Spontaneous Bleeding Episodes: Bleeding episodes should be classified as spontaneous if a subject records a bleeding event when there is *no known* contributing factor such as definite trauma, antecedent "strenuous" activity, or "overuse". The determination of "strenuous" or "overuse" is at the discretion of the subject/caregiver/investigator. For example, if a subject were to wake up in the morning and note he was bleeding, a "spontaneous" bleed would be recorded. Target joints can have spontaneous bleeding episodes. Incidences of spontaneous

bleeding episodes define regimen escalation criteria during prophylaxis (see Section 15.3.3). For this purpose, spontaneous bleeds are further categorized as "significant". Significant spontaneous bleeds are defined as those that lead to a transient or persistent loss of function (see Section 15.3.3).

*Traumatic Bleeding Episodes*: Bleeding episodes should be classified as traumatic if a subject records a bleeding event when there is a known or presumed reason for the bleed. For example, if a subject were to exercise strenuously and then have a bleed in the absence of any obvious injury, the bleed would be recorded as a traumatic bleed. Target joint bleeding episodes can be traumatic if a known action led to bleeding into the joint.

## 18.1.2. Location of Bleeds

For the purposes of this study, when subjects report a bleed treated with study drug, the location of the bleed should be recorded in the Subject Diary or medical record. Bleeds will be reported as occurring in 1 of the following locations: joint, muscle/soft tissue, or other. Each individual location of multiple-site bleeds will be reported. For joint bleeds, the specific joint will be reported. Parameters to identify joint bleeds include: pain on joint motion, limitation of motion, and visible swelling of joint.

#### 18.1.3. Treatment of Bleeds

Typically, a bleed would be treated with an (on-demand) infusion of study drug. The specific treatment with study drug is at the discretion of the subject/caregiver/investigator but all doses and infusions of study drug will be recorded and reported.

The subject/caregiver/investigator will assess efficacy of study drug in treating a bleed by recording their assessments of efficacy through the use of the 4-point On-Demand Hemostasis Efficacy Rating Scale, described below. The 4-point response scale for on-demand treatment of a bleeding episode, is defined as follows:

- *Excellent*: Definite pain relief and/or improvement in signs of bleeding starting within 8 hours after an infusion, with no additional infusion administered.
- Good: Definite pain relief and/or improvement in signs of bleeding starting within 8 hours after an infusion, with at least one additional infusion administered for complete resolution of the bleeding episode.

or,

Definite pain relief and/or improvement in signs of bleeding starting after 8 hours following the infusion, with no additional infusion administered.

• *Moderate*: Probable or slight improvement starting after 8 hours following the infusion, with at least one additional infusion administered for complete resolution of the bleeding episode.

• *No Response*: No improvement at all between infusions or during the 24 hour interval following an infusion, or condition worsens.

# 18.2. Less Than Expected Therapeutic Effect

All bleed and study drug infusion response data will be reported and analyzed (see Sections 22.2 and 22.5.3). The following text describes criteria defining a specific subset of these data that will also be reported and referred to "Less than expected therapeutic effect".

"Less than expected therapeutic effect" (LETE) is an efficacy variable of this study. LETE can occur in 3 specific circumstances. *All* types of LETE in aggregate and individually will be summarized as part of the efficacy information collected in this study. The following criteria define LETE.

Less than Expected Therapeutic Effect in the On-Demand Setting

LETE occurs in the on-demand setting if the subject records 2 successive "*No Response*" ratings after 2 successive study drug infusions, respectively. The infusions must have been administered within 24 hours (≤24 hours) of each other for treatment of the same bleeding event in the absence of confounding factors (described below). Therefore, LETE in the on-demand setting is based on the *response* to treatment of a bleed. The only confounding factors are as follows:

- Known presence or subsequent identification of a FVIII inhibitor.
- Known inadequate dose for the type and/or severity of bleed in the opinion of the investigator.
- Delay of greater than 4 hours between onset of bleed to infusion.
- Delay of greater than 24 hours before administration of a follow-up infusion.
- Known compromised study drug.
- Faulty administration of study drug.
- The subject has an underlying, predisposing condition responsible for the bleed in the opinion of the investigator (eg, kidney stones or use of medications known to impair platelet function, such as aspirin or NSAIDs).

For the purposes of this study, LETE in the on-demand setting will be summarized only from eCRFs. In the absence of identified confounding factors, monitors will query a site if 2 "*No Response*" ratings occur for 2 infusions which are given within 24 hours (≤24 hours) for the same bleed and LETE is not noted.

Less than Expected Therapeutic Effect in the Prophylaxis Setting

LETE occurs in the prophylaxis setting if there is a *spontaneous* bleed within 48 hours ( $\leq$  48 hours) after a regularly scheduled prophylactic dose of study drug (which was not used to treat a bleed) in the absence of confounding factors. Therefore, LETE in the prophylaxis setting is the *occurrence* of a bleed. The only confounding factors are as follows:

- Known presence or subsequent identification of a FVIII inhibitor.
- Known inadequate prophylactic dose (ie, a dose less than that prescribed in subject's regimen).
- Known lack of adherence to the prescribed prophylaxis regimen.
- Bleed occurs in a target joint identified at the start of the study.
- Known compromised study drug.
- Faulty administration of study drug.
- The subject has an underlying, predisposing condition responsible for the bleed in the opinion of the investigator (eg, kidney stones or use of medications known to impair platelet function, such as aspirin or NSAIDs).

For the purposes of this study, LETE in the prophylaxis setting will be summarized only from eCRFs. In the absence of identified confounding factors, monitors will query a site if a spontaneous bleed within 48 hours (≤48 hours) of a prophylactic dose is recorded and LETE is not noted.

Less than Expected Therapeutic Effect (Low Recovery)

LETE can also be lower than expected recovery of FVIII in the opinion of the investigator following infusion of study drug in the absence of confounding factors. There are no planned recovery measurements outside the PK assessment that subjects may undergo at study start. During the course of this study, additional recovery measurements should be done only for assessment of a possible FVIII inhibitor. (NOTE: During the treatment phase of the study, all tests for FVIII:C and/or FVIII inhibitor performed at the local laboratory should have duplicate samples from the same phlebotomy shipped to the central laboratory for analyses.) Therefore, LETE (Low Recovery) can happen only if a recovery measurement is performed for clinical management of a subject and an inhibitor is not confirmed by the central laboratory. The only confounding factors for low recovery are as follows:

- Known presence or subsequent identification of a FVIII inhibitor.
- Known compromised study drug.
- Faulty administration of study drug.

#### 19. PHARMACOKINETICS

# 19.1. Pharmacokinetic Analysis

FVIII:C will be analyzed by a central laboratory using a one-stage method (mnemonic CB-0052). Using a sample volume of 0.5 mL, the range of quantitation is 0.0100-0.8300 IU/mL. The upper limit of quantitation is slightly variable and depends upon the potency of the lot of calibrator. Stability of the samples has been shown for 3 freeze/thaw cycles. The coefficient of variations for precision of the calibrators in method development was less than 12.4% and the accuracy ranged between 89 and 115% of the expected amount.

#### 19.2. Pharmacokinetic Methods

The plasma FVIII activity (FVIII: C)-versus-time curves after administration of moroctocog alfa (AF-CC) will be characterized, using standard noncompartmental methods. FVIII:C at 0.5 hours after the start of study drug infusion ( $C_{0.5\,hr}$ ) will be directly determined from the observed FVIII:C data. The terminal-phase disposition (elimination) rate constant ( $\lambda_z$ ) will be estimated by regression of the terminal log-linear phase of the FVIII:C-versus-time curve. The terminal phase half-life ( $t_{1/2}$ ) will be calculated as:

$$t_{1/2} = \ln 2 / \lambda_z$$

The areas under the FVIII:C-versus-time curves ( $AUC_t$ ) and under the moment curve ( $AUMC_t$ ) to last measurable activity ( $C_t$ ) will be calculated using the trapezoidal method.

The area under the curve from 0 to infinity (AUC $_{\infty}$ ) will be estimated as:

$$AUC_{\infty} = AUC_t + C_t / \lambda_z$$

Similarly, area under the moment curve from 0 to infinity (AUMC $_{\infty}$ ) will be estimated as:

$$AUMC_{\infty} = AUMC_t + \left[ \left( C_t \times t \right) / \lambda_z \right] + \left[ C_t / \left( \lambda_z \right)^2 \right]$$

where, t is the time corresponding to the last measurable Ct.

The clearance (CL) will be calculated as:

$$CL = Dose/AUC_{\infty}$$

where, Dose = IU/kg of study drug administered.

The mean residence time (MRT) will be calculated as:

$$MRT = AUMC_{\infty}/AUC_{\infty} - TI/2$$

where, TI is the duration of infusion.

The volume of distribution at steady state  $(V_{ss})$  will be calculated as:

$$V_{ss} = CL \times MRT$$
.

Incremental recovery, is estimated using the following formula:

Incremental recovery =  $(C_{0.5 \text{ hr}}-C_0)/Dose$ 

where,

 $C_0$  = FVIII:C at time 0 (time before start of study drug infusion)

Dose = IU/kg of study drug administered.

The FVIII:C concentrations measured in this study may be combined with similar data from other studies to perform a population pharmacokinetic analysis using nonlinear mixed effects modeling (NONMEM).

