During prophylaxis, a subject's treatment will be escalated to a higher intensity prophylaxis regimen comprised of the most intensive components of both regimens A and B ( $45 \pm 5 \text{ IU/kg}$ , administered every other day) if criteria justifying regimen escalation are met: over a 4-week period, the occurrence of 2 or more spontaneous joint bleeds or the occurrence of 3 or more spontaneous bleeds (consisting of joint bleeds, and/or significant soft tissue/muscle or other site bleeds). Subjects who meet dose escalation criteria while on this more intensive regimen may dose escalate to a higher intensity regimen designated by the investigator. During prophylaxis, subjects will also use moroctocog alfa (AF-CC), as needed, for the treatment of bleeds (ie, on-demand), should they occur.

Clinical and laboratory examinations, including assessments for FVIII inhibitor development, will be conducted during the course of the study.

Moroctocog alfa (AF-CC) efficacy and safety will be assessed over the entire treatment period.

A subset of subjects may participate in assessments for FVIII PK characterization after administration of moroctocog alfa (AF-CC). This subset of subjects will undergo a baseline PK assessment, receiving a single open-label dose of moroctocog alfa (AF-CC) ( $50 \pm 5$  IU/kg, rounded to the closest complete vial) with blood sampled for FVIII activity measurements before and at 0.5, 8, 24, 28 (optional), and 32 hours after the start of infusion.

**Main Inclusion Criteria:** Males  $\geq 6$  months to < 16 years of age at the time of screening visit with moderately severe to severe hemophilia A (FVIII activity  $\leq 2\%$ ), with previous FVIII replacement therapy experience ( $\geq 20$  exposure days).

Main Exclusion Criteria: Current or history of FVIII inhibitor.

Concomitant Treatment: Regular medication, other than FVIII concentrates, may continue unchanged.

**Test Articles(s) and Administration:** Moroctocog alfa (AF-CC) study drug; single 50 ±5 IU/kg (rounded to closest complete vial) intravenous infusions administered for PK assessment; either 45 IU/kg twice per week or 25 IU/kg every other day for prophylaxis treatment (or according to investigator prescription in the event that escalation criteria are met while the subject is practicing the initial protocol-defined escalated regimen).

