To achieve its objectives, this study evaluates moroctocog alfa (AF-CC) in the context of two settings. A cohort of subjects was enrolled who practiced on-demand therapy for a 6-month period during segment 1, then switched to prophylaxis with moroctocog alfa (AF-CC) for a 12-month period in segment 2, practicing a protocol-defined regimen (25 ±5 IU/kg, administered every other day). This regimen has been well characterized and has demonstrated efficacy relative to on-demand therapy, although in a different patient population. A second cohort, comprising all other subjects, will practice a single moroctocog alfa (AF-CC) treatment modality, prophylaxis, during this study, but treatment

will include practice of each of the two protocol-defined regimens; these subjects will follow one of the two randomly assigned protocol-defined regimens for a 12-month period (segment 1), and then will crossover to the other regimen for a second 12-month treatment period (segment 2). Study subjects will be hereafter referred to by their segment 1 treatment modality: on-demand (OD) subjects and routine prophylaxis (RP) subjects. This study design allows direct evaluation of moroctocog alfa (AF-CC) in the prophylaxis and on-demand settings, as well as a direct comparison between 2 different moroctocog alfa (AF-CC) prophylaxis-dosing schedules. The duration of moroctocog alfa (AF-CC) treatment in this study (18 - 24 months depending on the cohort) ensures that sufficient experience with moroctocog alfa (AF-CC) is obtained.

Pharmacokinetic assessment of FVIII:C after FVIII therapy has shown lower FVIII:C recovery, in young children. For moroctocog alfa, this has also been observed: a mean incremental recovery of  $1.5 \pm 0.6$  IU/dL per IU/kg, in 59 children with median age  $10 \pm 8.3$  months was reported compared with mean incremental recovery of  $2.4 \pm 0.4$  IU/dL per IU/kg in 101 patients with a median age of  $26 \pm 12$  years. Younger patients also have higher clearance, when adjusted for body size and shorter half-lives compared with older children and adults. A secondary objective of this study is to continue to characterize the pharmacokinetics of moroctocog alfa (AF-CC) in pediatric patients. To achieve this objective, a subset of enrolled subjects will participate in a pharmacokinetic assessment conducted at the start of the study.

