#### 11. STUDY DESIGN

# 11.1. Description

There will have been two cohorts enrolled into the study; one in which the subject practices on-demand therapy for the first segment of the study, followed by routine prophylaxis for the second segment, and, another cohort in which the subject practices routine prophylaxis for both segments. Study subjects will be hereafter referred to by their segment 1 treatment modality: on-demand (OD) subjects and routine prophylaxis (RP) subjects. Enrollment into the OD cohort has been closed. Enrollment for the RP cohort is ongoing.

Enrollment for the RP cohort will continue and will be conducted as an open-label, multicenter trial of moroctocog alfa (AF-CC) in approximately 56 subjects (≥6 months to <16 years of age) with moderately severe to severe hemophilia A. The study will be conducted in two 12-month segments (Also refer to Section 6).

At study start, a subset of subjects may participate in optional assessments to characterize the PK of FVIII after moroctocog alfa (AF-CC) administration. Subjects who are eligible and opt to participate will undergo a baseline PK assessment, receiving a single open-label dose of moroctocog alfa (AF-CC) ( $50 \pm 5 \text{ IU/kg}$  rounded to the nearest complete vial) with blood sampled for FVIII activity measurements before and at 0.5, 8, 24, 28 (optional), and 32 hours after the start of the infusion.

All RP subjects will practice prophylaxis with moroctocog alfa (AF-CC) according to 1 of 2 randomly assigned moroctocog alfa (AF-CC) regimens, each delivering approximately 90 IU/kg/week, but differing in dosing schedule. Randomization will be stratified by hemophilia A severity: FVIII activity <1% or 1-2% (central laboratory screening result). Each segment will be 12 months in duration.

In the first segment, subjects will be randomly assigned to Regimen A:  $45 \pm 5$  IU/kg, administered twice per week or Regimen B:  $25 \pm 5$  IU/kg, administered every other day.

For regimen A, the interval between prophylactic infusions should be 3 to 4 days, and should not exceed 4 days. For regimen B, the interval between prophylactic infusions should be approximately 48 hours (eg, an appropriate dosing schedule for Regimen B is as follows Monday, Wednesday, Friday, Sunday, Tuesday, Thursday, Saturday, Monday...etc).

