The subject will receive a single  $50 \pm 5$  IU/kg, rounded to the nearest vial, intravenous (IV) infusion of moroctocog alfa (AF-CC), given over no more than 2 minutes. The time of study drug reconstitution will be recorded. The dose, prepared from a single lot, will be calculated based on the subject's actual body weight as measured that day (see Study Reference Manual for specific guidelines for PK dose based on the subject's measured body weight). The start and stop time of the infusion will be recorded. The residual volume of dose remaining in the tubing, if any, should be immediately flushed into the subject as described in the Study Reference Manual. Time 0 is the time when the study drug infusion begins.

Blood samples for FVIII:C determinations, to be used for PK analysis, will be drawn at 0.5 hours ( $\pm 3$  minutes), 8 hours ( $\pm 48$  minutes), 24 hours ( $\pm 1$  hour), 28 hours ( $\pm 1$  hour), and 32 hours ( $\pm 1$  hour) after the start of the study drug infusion (refer to study flow chart in Section 8). The blood sample to be drawn at 28 hours is optional. The exact times of the actual PK sample blood draws will be recorded in the source documents. All samples collected during the PK assessment must be prepared and identified in the manner described in the Study Reference Manual.

Just before (ie, within approximately 20 minutes of) the 0.5 and 24-hour PK sample collection times, vital signs (including temperature [Celsius], blood pressure, pulse, and respiration) will be collected.

Any AEs and concomitant medications should be recorded throughout the PK assessment in the subject's source document.

If a subject experiences a bleeding episode during the PK assessment, the subject is to be stabilized with study drug. The samples collected should be processed as directed.

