2.1. Pharmacokinetic Endpoints

The primary PK variables will be terminal phase half-life $(t_{1/2})$, incremental recovery (K-value), and clearance (CL). Secondary PK variables will include: maximum concentration (FVIII:C at 0.5 hours after study drug infusion $[C_{0.5 \text{ hr}}]$), area under the curve to infinity (AUC $_{\infty}$), area under the curve to last measurable concentration (AUC $_{v}$), steady-state volume of distribution (V_{SS}), and mean residence time (MRT).

Summaries for each of these variables will be reported for the PK assessment to characterize the single-dose PK of moroctocog alfa (AF-CC) at initial exposure.

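### The trapezoid rule for AUC and AUMC is left open; read as linear on this sparse schedule, it understates clearance and Vss, most at short half-lives

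*Protocol*

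**What the plan says.** Protocol 11.1 and the synopsis give the PK schedule: "blood sampled for FVIII activity measurements before and at 0.5, 8, 24, 28 (optional), and 32 hours after the start of the infusion". Protocol 15.2 confirms that "The blood sample to be drawn at 28 hours is optional".

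Protocol 19.2 states that the areas under the concentration and moment curves "will be calculated using the trapezoidal method". It names no variant of the rule and does not say what concentration stands at time 0 after the bolus. The tail is added as C_t/λz. CL is Dose/AUC∞, MRT is AUMC∞/AUC∞ less half the infusion time, and Vss is CL × MRT, so all three inherit any error in the areas.

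SAP 2.5 refers back to the protocol for the noncompartmental method, and SAP 2.6 names the software but not its interpolation setting. SAP 2.1 lists half-life as a primary PK variable together with "incremental recovery (K-value), and clearance (CL"). Protocol 22.5.4 plans graphs of age and body size against CL, Vss, half-life and incremental recovery. Protocol 9.4 says: "Younger patients also have higher clearance, when adjusted for body size and shorter half-lives compared with older children and adults". No half-life in hours appears in either document.

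**The concern.** A straight line drawn between two points on an exponentially falling curve lies above the curve. The wider the interval relative to the half-life, the larger the excess. Here two intervals are wide: 7.5 hours and 16 hours.

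The protocol itself expects half-life to be shorter in younger children, so the error would follow age rather than average out. At stake is the descriptive account of paediatric PK, a stated secondary objective: clearance and Vss would be too low, and lowest relative to truth in the youngest. The protocol reports higher clearance and lower recovery (which suggests a larger volume per kg) in young patients, so understating both most in that group would make the age gradient look shallower than it is.

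**Working it through.** The documents give no AUC or CL figure to reproduce, so this is a numerical check of the rule on a known curve.

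**Inputs**
- Sampling times 0.5, 8, 24 and 32 h, with and without 28 h (Protocol 11.1, 15.2).
- AUC∞, AUMC∞, CL, MRT and Vss formulas (Protocol 19.2). The infusion lasts at most 2 minutes, so half the infusion time is ignored.
- Assumption: C(t) = exp(-kt), k = ln 2 / half-life, with half-life 6 to 12 h. True AUC∞ = 1/k, true MRT = 1/k, true Vss = 1 in these units.
- Time 0 taken two ways: pre-dose value of 0, or back-extrapolated to 1.

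**Single interval.** Over an interval of length d, linear area / exact area = x·coth(x), with x = kd/2. For 8-24 h, x = 8k. The ratio is 1.270 at a half-life of 6 h, 1.155 at 8 h, 1.100 at 10 h and 1.070 at 12 h.

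**Worked case, half-life 8 h, pre-dose 0.** k = 0.08664. C = 0.9576, 0.5, 0.125 and 0.0625 at 0.5, 8, 24 and 32 h.
- 0-0.5 h: 0.5 × 0.9576/2 = 0.239
- 0.5-8 h: 7.5 × (0.9576 + 0.5)/2 = 5.466
- 8-24 h: 16 × (0.5 + 0.125)/2 = 5.000 (exact 4.328)
- 24-32 h: 8 × (0.125 + 0.0625)/2 = 0.750
- tail: 0.0625/0.08664 = 0.721

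AUC∞ = 12.177 against 1/k = 11.542, or +5.5%. CL is 11.542/12.177 - 1 = -5.2%. The same steps for AUMC∞ give 124.32 against 1/k² = 133.21. MRT = 124.32/12.177 = 10.21, or -11.5%, and Vss = 10.21/12.177 = 0.838, or -16.2%.

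**Linear rule, bias against truth**

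| Half-life | AUC∞, pre-dose 0 | CL | Vss | AUC∞, back-extrapolated | CL | Vss |
|---|---|---|---|---|---|---|
| 6 h | +9.8% | -8.9% | -23.5% | +12.7% | -11.2% | -27.4% |
| 8 h | +5.5% | -5.2% | -16.2% | +7.7% | -7.1% | -19.5% |
| 10 h | +3.2% | -3.1% | -11.0% | +5.0% | -4.7% | -13.9% |
| 12 h | +1.9% | -1.9% | -7.6% | +3.4% | -3.3% | -10.1% |

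The 28 h sample changes AUC∞ by at most 0.2 percentage points.

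**Where the error arises (share of true AUC∞, half-life 12 h to 6 h).** The 8-24 h interval adds 2.7% to 9.0%, and 0.5-8 h adds 0.5% to 3.4%. A pre-dose zero takes away 1.4% to 2.9% in the first half hour.

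**Effect on an age contrast.** A true two-fold CL difference (6 h against 12 h, equal volume) appears as 2 × 0.911/0.981 = 1.86-fold under the linear rule with pre-dose 0.

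**Log-down rule.** With a back-extrapolated time 0 the bias in AUC∞, CL and Vss is 0.0% throughout for this model. With pre-dose 0 it reverses: AUC∞ is 1.4% to 2.9% too low, CL 1.5% to 3.0% too high and Vss 3.0% to 6.0% too high.

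**Sensitivity.** Bi-exponential curves (fast fraction 20-30%, fast half-life 1.5 or 3 h, terminal half-life 6-12 h) keep the direction: linear AUC∞ +3.3% to +18.2%, CL -3.2% to -15.4%. Log-down with back-extrapolation leaves AUC∞ about 0.5% to 3% high. Over a wider mono-exponential range the linear AUC∞ bias with pre-dose 0 runs from +0.1% at 20 h to +18.2% at 4 h. At 3 h it is +11.7%, because the 24 h value falls below the 0.01 IU/mL quantitation limit and the 8-24 h interval drops out.

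**The case against.** The strongest reply is that neither document says linear. Protocol 19.2 speaks of standard noncompartmental methods, and the validated software may have been set to log-down. That stands. A reader might infer that the trial's AUC is in fact too high and its clearance too low; the documents do not support this, because the setting is not stated. They support a conditional statement: the plain reading of an unqualified trapezoid is the straight-line one, and under it the bias follows.

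The sizes also depend on an assumed half-life and a noise-free curve. That stands too: the AUC figure varies about fivefold between 6 and 12 h.

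Two further readings should be resisted. Comparing CL under the linear rule with CL under the log rule (both with pre-dose 0) gives a gap of 3.3% to 11.5%. That is not the understatement of clearance, since the log result there errs the other way. Nor is the 8-24 h gap the sole cause: 0.5-8 h contributes as well, and equals or exceeds it in some of the curves with a marked distribution phase.

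Finally, PK is descriptive, age is examined only in graphs, and half-life and incremental recovery do not use AUC. All true, and this limits the importance. It does not remove a half-life-dependent error in a primary PK variable. The optional population PK model in Protocol 19.2 would not correct the reported noncompartmental values.

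**Conclusion.** The point holds in conditional form and is minor. The plan leaves both the interpolation rule and the time-0 value open on a schedule where they matter. Under the linear reading, with mono-exponential decline and an assumed half-life of 6 to 12 h, clearance is understated by about 2-9% and Vss by about 8-23% with pre-dose 0 at time 0, or by 3-11% and 10-27% with back-extrapolation. The error is largest at short half-lives and so, on the protocol's own account, in the youngest children. It would moderately flatten the clearance and Vss plots against age. No test, power or error rate is affected. Describing the PK results as wrong, or the PK objective as lost, would go beyond the documents.

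**What to change.** In Protocol 19.2 or SAP 2.5, specify linear-up/log-down trapezoids for both AUC and AUMC, together with a back-extrapolated concentration at time 0 after the bolus. Both parts are needed, because log-down with a pre-dose zero leaves a smaller age-related bias of opposite sign. Then rerun the noncompartmental analysis on the collected profiles. If the linear rule was used for the interim report, show CL and Vss both ways.

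The cost is a sentence or two of text, a change of software settings and a rerun. No new samples are needed. The drawback is that CL, MRT and Vss may differ slightly from the interim figures and will need a line of explanation.
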